5.3.2 Key Secondary Efficacy Variable

The analysis of the key secondary efficacy measure, CGI-C, will be performed using ANCOVA, with age (at 2 levels: <10, ≥10 years), sex, treatment, region, visit, and treatment-by-visit interaction as fixed effects (at Visit 9 [“Month 6”]). The estimate of the treatment effect parameter, together with the associated two-sided 95% CI and p value will be calculated.

The primary analysis of CGI-C will impute missing values using LOCF. Additional sensitivity analyses will be performed with missing values imputed using Multiple Imputation Method 1 (as described in [Section 5.1.3](#)) and OC.

For the extension treatment period the same ANCOVA model will be used to estimate the treatment effect for the CGI-C at Visit 12 (“Month 9”) and Visit 15 (“Month 12”). Missing data will be imputed using LOCF. Sensitivity analyses will be performed using ANCOVA based on OC.

If the normality assumption of ANCOVA is not met, the alternative methodology of rank score ANCOVA will be used.

Sensitivity analyses of CGI-C will also be performed using a proportional odds model with ordinal logistic regression with age (at 2 levels: <10, ≥10 years), sex, treatment, region, visit, and treatment-by-visit interaction as fixed effects (at Visit 9 [“Month 6”]). The estimate of the treatment effect odds ratio, together with the associated two-sided 95% CI and p value, will be calculated. The primary analysis will impute missing value using LOCF, and additional analyses will be performed with missing values imputed using Multiple Imputation Method 1 (as described in [Section 5.1.3](#)) and OC.

In addition, the proportion of subjects with improvement or stable disease (scores of 1, 2, 3, or 4), versus those with worsening (scores of 5, 6, or 7) at Visit 9 will be compared between the EDS-EP high and low doses versus placebo by using a logistic regression model with fixed effects for age, sex, region, and treatment. For the extension treatment period, the same analysis will be repeated at Visit 15 (“Month 12”). Odds ratios and the associated 95% confidence intervals will be reported. Missing values will be imputed using LOCF. Sensitivity analyses will include logistic regression

based on OC. These analyses will be repeated comparing the proportion of subjects with improvement (scores of 1, 2, or 3) versus those with stable or worsening (scores of 4, 5, 6, or 7).

CGI-C scores at all the visits during the initial treatment period and the extension treatment period (Visit 6, Visit 9, Visit 12, and Visit 15) will be summarized using summary statistics appropriate for the analysis (that is, for continuous or categorical data) by treatment group.

For the FAS only, the mean CGI-C score will be plotted over time during the initial treatment period with separate trend lines for each of the three treatment groups. This type of plot will be repeated for mean CGI-C score over the entire study, with separate trend lines for the seven possible dosing schemes.

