At Baseline (Day 0/1), vital signs and physical and neurological examinations will be repeated and the Columbia-Suicide Severity Rating Scale (C-SSRS) will be performed. The inclusion/exclusion criteria will be reviewed and patients meeting all criteria will be randomized to one of the 3 treatment groups. Two ratings will be done on the ICARS, one 24 hours before baseline (Day 0) and the other on Day 1 (pre-dose); video recording will be required for both assessments. In addition, the baseline ratings of the following efficacy measures will be performed prior to dosing: CGI-S (assess baseline severity of the patient for use in evaluating change at post-baseline visits), VABS, and EQ-5D-5L. The diverted blood sample (see [Section 11.6](#), at least 15 mL, will be drawn prior to dosing to measure baseline values for the foreseen laboratory tests. The serum and urine pregnancy test will be repeated for women of childbearing potential. A baseline measurement of bone mineral density (BMD) will be performed.

Initial Treatment Period (6 months)

CCI

To maintain the blind, all properly prepared RBCs (EDS or Placebo) will be administered to the patients, without knowledge of the actual dose or treatment being administered.

CCI

On Day 1, a blood sample will be collected for measurement of free plasma hemoglobin, 1 hr post-infusion. On Days 2 and 15, a complete hemolysis panel [free plasma hemoglobin, haptoglobin, bilirubin (total and conjugated), CBC, LDH, urinalysis] will be performed.

At Months 1, 2, 3, 4 and 5, a blood sample will be taken for dexamethasone PK before and 1 hr after the infusion (except for Month 1). Measurement of body weight and height in triplicate, as well as a C-SSRS assessment, will be performed at each of these visits. The diverted blood sample (see [Section 11.6](#)) will be collected for measurement of serum creatinine at Months 1, 2, 4 and 5, whereas creatinine will be part of the routine laboratory tests at Months 3 and 6. Upon completion of the EDS process, 2.5 mL of the treated blood will be collected for measurement of DSP concentration and a CBC. At Month 3, in selected centers, a 5-mL sample will be taken from the EryKit_01 bowl at the end of the process to assess RBC osmotic resistance.

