The primary efficacy variable, change from baseline in ‘Modified’ ICARS total score, will be analyzed using a Mixed Model Repeated Measures (MMRM) approach, with the baseline value as covariate and age, treatment, region, baseline value and treatment interaction, visit and treatment-by-visit interaction as fixed effects. The estimated treatment difference, together with the associated two-sided 95% CI and p-value, will be calculated. Unstructured covariance matrices will be used. Model effect estimation will be based on restricted maximum likelihood (REML). The region and treatment interaction can be tested in a separate model and if a significant interaction is found, then forest plot will be used to present the region specific treatment difference and associated 95% confidence interval.

The primary MMRM analysis will assume missing at random (MAR) as a means of handling missing data. Sensitivity analyses will be performed to evaluate the MAR assumption. For this, ANCOVA with missing data imputed using Last Observation Carried Forward (LOCF), Observed Case (OC), and OC + RDO will be used.

Analysis of the Key Secondary Efficacy Parameter

The analysis of the key secondary efficacy measure, CGI-C, will be performed using ANCOVA, with age, sex, treatment, region, visit and treatment-by-visit interaction as fixed effects. The estimate of the treatment difference parameter, together with the associated two-sided 95% CI and p-value at will be calculated.

In this analysis, LOCF will be used for missing data. Sensitivity analyses will use OC, OC + RDO for imputing missing values.

Hypothesis Testing and Handling of Multiple Comparisons

The ~14-22 mg dose of the primary efficacy end point will be tested at the two-sided significance level of 0.05. With this requirement, the overall family-wise error rate (FWER) can be no greater than 0.05 two-sided. The study will be judged statistically significant if the ~14-22 mg dose of the primary efficacy endpoint is significant.

The ~5-10 mg dose of the primary efficacy endpoint will be tested only if the ~14-22 mg dose is found to be statistically significant compared to placebo. In this way, the 0.05 two-sided significance level will be maintained and no adjustment will be necessary.

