5.3.1 Primary Efficacy Variable

The modified ICARS total score from the central rater (with speech domain scores from local raters) at baseline and each follow-up visit, and the change and percent change from baseline to each follow-up visit, will be summarized using descriptive summary statistics by treatment group.

The primary efficacy variable, change from baseline to follow-up (Visit 6 [“Month 3”] and Visit 9 [“Month 6”]) in mICARS total score (described above), will be analyzed using a mixed model repeated measures (MMRM) analysis, with the baseline mICARS value as covariate and five fixed effects (treatment, age [6 to <10 years, ≥ 10 years], sex, region, visit) and one interaction term (treatment-by-visit). The treatment effect, together with the associated two-sided 95% CI and p-value will be calculated. Unstructured covariance matrices will be used. Model effect estimation will be based on restricted maximum likelihood (REML). The region-by-treatment interaction can be tested in a separate model and if a significant interaction is found, then a forest plot will be used to present the region-specific treatment effects and associated 95% confidence intervals.

The primary MMRM analysis will assume missing at random (MAR) as a means of handling missing data.

Sensitivity analyses of these primary analyses will consist of ANCOVA at Visit 9 (‘‘Month 6’’) with missing data imputed using multiple imputations as described in [Section 5.1.3](#), LOCF, and OC. The results from each of the sensitivity analyses will be compared to the primary MMRM analysis.

When applying the multiple imputation methods describe in [Section 5.1.3](#), the regression method will be used, and the imputation model will be the same as the analysis model, based on the factors treatment, sex, age (category), region, and baseline mICARS; the pattern of missing data will be essentially monotonic since none of the factors used in the model are expected to be missing. One hundred iterations of the model will be run, and the results will be combined with SAS PROC MIANALYZE. For Multiple Imputation Method #2, multiple imputation based on subjects taking the same treatment will be applied first to the missing data due to COVID-19 related restrictions, and then Jump to Reference will be applied to the remaining missing data.

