5.3.3 Other Secondary Efficacy Variables

CGI-S (structured)

The analysis of the change from baseline to Visit 9 (“Month 6”) of CGI-S (structured) score will be performed similar to the analysis of the CGI-C score, modifying the approach using baseline as a covariate. The analysis for the extension treatment period will be performed in a similar way. For the extension treatment period, the change from baseline will be the change from the last assessment prior to first infusion in the study except for the placebo subjects who switch to EDS-EP at Visits 9 and 12 (“Month 6” and “Month 9”, respectively). For these subjects who are switched, the baseline will be the assessment just prior to the switch.

Ordinal logistic regression analyses will also be performed for CGI-S (structured) in a manner similar to CGI-C, with the exception that baseline CGI-S (structured) score will enter into the analysis.

The CGI-S score at baseline and all visits during the initial treatment period and extension treatment period (Visit 6, Visit 9, Visit 12, and Visit 15) will be summarized using summary statistics appropriate for continuous or categorical data by treatment group. The change from baseline to all visits will also be summarized and compared between treatment groups. Percent change from baseline will be summarized descriptively.

For the FAS only, the mean CGI-S score will be plotted over time during the initial treatment period with separate trend lines for each of the three treatment groups. This type of plot will be repeated for mean CGI-S score and mean change from baseline in CGI-S score over the entire study, with separate trend lines for the seven possible dosing schemes.

VABS

The analysis of the change from baseline (Day 0) to Visit 9 (“Month 6”) of VABS score will be performed using ANCOVA with LOCF score from baseline to Visit 9 (“Month 6”). Sensitivity analyses will be based on OC. The analysis for the extension treatment period will be performed in the same way. For the extension treatment period, the change from baseline will be the change from the last assessment prior to first infusion in the study except for the placebo subjects who switch to EDS-EP at Visits 9 and 12 (“Month 6” and “Month 9”, respectively). For these subjects who are switched, the baseline will be the assessment just prior to the switch.

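### The key secondary CGI-C models adjust for age category, sex and region but for no baseline severity measure, which may cost precision on an endpoint that gates the low-dose mICARS test

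*SAP*

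**What the plan says.** SAP 5.3.2 gives the main model for the key secondary endpoint: "CGI-C, will be performed using ANCOVA, with age (at 2 levels: <10, ≥10 years), sex, treatment, region, visit, and treatment-by-visit interaction as fixed effects". Protocol 16.2.8, under the analysis of the key secondary parameter, agrees: "CGI-C, will be performed using ANCOVA, with age, sex, treatment, region, visit and treatment-by-visit interaction as fixed effects". Every term is a factor and none measures how severe the disease was at entry. The proportional-odds model in SAP 5.3.2 repeats the list. The two logistic models there use age, sex, region and treatment.

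The neighbouring endpoints are handled differently. The primary model in SAP 5.3.1 is fitted "with the baseline mICARS value as covariate and five fixed effects". SAP 5.3.3 analyses CGI-S like CGI-C, "modifying the approach using baseline as a covariate", and fits its ordinal model "with the exception that baseline CGI-S (structured) score will enter into the analysis".

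The data are planned. CGI-S and ICARS are both scheduled at screening and at baseline. SAP 5.1.3 substitutes the screening value when the baseline value is missing, and SAP Section 4 gives an ICARS fallback from Day 1 to Day 0 to the local screening score. Minimisation uses sex, age group and region (SAP 1.2 and 5.1.8), not severity.

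**The concern.** A baseline measure that predicts the outcome reduces residual variance when it enters the model, and it adjusts the comparison for whatever chance difference in that measure the arms show. Here two candidates are already scheduled, the plan uses baseline values for the endpoints on either side of CGI-C, and the randomisation does not balance severity directly.

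CGI-C matters beyond its own result. Under SAP 5.1.10, low-dose mICARS is tested only if high dose succeeds on both mICARS and CGI-C. Avoidable imprecision in CGI-C therefore also lowers the chance of reaching a second confirmatory test. No power, effect size or standard deviation is stated for CGI-C, so the plan does not show that there is precision to spare.

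**Working it through.** The plan states no figure for CGI-C that could be reproduced; SAP Table 3 covers mICARS only. The check is therefore the gain from one covariate, over a range of assumed correlations.

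**Inputs**
- 175 patients randomised 1:1:1 (SAP 1.2): 175/3 = 58.3, about 58 per arm. The high-dose versus placebo contrast has 175 × 2/3 = 116.7, about 117.
- r: partial correlation of baseline severity with Month 6 CGI-C, given age category, sex and region. It is not in the documents and is assumed.
- Two-sided 0.05 (SAP 5.1.10).

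**Precision**

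Adjusted variance = (1 − r²) × unadjusted variance. SE reduction = 1 − √(1 − r²). Patient equivalent = 117/(1 − r²) − 117. The last column assumes 80% power before adjustment.

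| r | SE reduction | Patients on 117 | 80% power becomes |
|---|---|---|---|
| 0 | 0% | 0 | 80.0% |
| 0.1 | 0.5% | 1.2 | 80.4% |
| 0.2 | 2.0% | 4.9 | 81.6% |
| 0.3 | 4.6% | 11.6 | 83.6% |
| 0.4 | 8.3% | 22.3 | 86.4% |

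**Chance imbalance**

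The SD of the standardised severity difference between two arms of 58 is √(2/58) = 0.186. A gap of at least 0.3 SD lies 0.3/0.186 = 1.62 SDs out, with two-sided probability 10.6%. This treats severity as unrelated to the minimisation factors, so it is an upper-end figure.

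Given a 0.3 SD gap, the unadjusted CGI-C difference shifts by 0.3 × r outcome SDs:
- r = 0.1: 0.03 SD, or 0.03/0.186 = 0.16 SE; type I error conditional on that gap is 5.2%.
- r = 0.3: 0.09 SD, or 0.48 SE; conditional type I error is 6.6%.

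For r = 0.3, the upper tail starts at (1.96 × 0.186 − 0.09)/(0.186 × √0.91) = 1.55 and contributes 6.1%. The lower tail contributes 0.5%.

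**Unconditional error**

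Simulating the unadjusted two-arm test with 58 per arm and no treatment effect (20,000 runs each) gave type I error of 5.3%, 5.4% and 4.7% at r = 0, 0.3 and 0.5. This is close to nominal whatever r is.

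**The case against.** The strongest objection is that r may be small. CGI-C is itself a rating of change from baseline, so it lacks the built-in link to a starting value that justifies baseline mICARS or baseline CGI-S in their own models. At r = 0.1 the gain is about one patient. This stands: loss of precision is possible and plausible, but the documents do not establish it.

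Second, severity is partly handled already. Protocol 7.3 says the minimisation is meant to reduce differences between arms in baseline symptoms. The same section reports severity rising with age below 10 years, and Protocol 12.2 reports higher CGI-S from age 10. Age category is both minimised and modelled. SAP 5.2.3 tabulates baseline ICARS and severity, and SAP 6.3.2 lists CGI-C subgroup tables. This also stands in part. However, Protocol 7.3 finds no such age correlation above 10 years, the model has only two age levels, and tables describe an imbalance without adjusting the main estimate for it.

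Third, a reader might take the protocol's reason for the baseline rating, "CGI-S (assess baseline severity of the patient for use in evaluating change at post-baseline visits", as naming a model covariate, and so conclude that the SAP ignores it on purpose. The sentence more naturally describes a reference point for the clinician who judges change. CGI-S has its own baseline and CGI-C does not, which is enough to explain the different treatment in SAP 5.3.3.

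Fourth, a reader might assume that a baseline value exists for every analysed patient. It is expected, not guaranteed: the FAS definition in SAP Section 2 requires no baseline value, and SAP 5.1.3 allows one to stay missing.

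**Conclusion.** The omission is real and consistent across the protocol, the SAP and every CGI-C model. It is a missed efficiency on a gatekeeping endpoint, not an error that invalidates the analysis. For assumed r between 0 and 0.4, adjustment would cut the standard error by 0% to about 8%, worth 0 to about 22 patients on roughly 117.

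Two stronger readings fail. One is that the unadjusted CGI-C estimate is biased or its type I error inflated. Under randomisation it is unbiased, and unconditional type I error stays near 5%; the shift arises only conditionally on an observed imbalance. The other is that severity imbalance goes wholly uncorrected. It is corrected as far as age category, sex and region capture severity, so the 11% chance of a 0.3 SD gap is an upper-end figure.

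The case for acting rests on low cost and on the gating role in SAP 5.1.10, not on a demonstrated loss.

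**What to change.** Before unblinding:

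- In SAP 5.3.2, add one pre-specified baseline severity covariate to the CGI-C ANCOVA and the rank ANCOVA: baseline structured CGI-S or baseline mICARS. The two overlap, and nothing in the documents justifies using both.
- Add the same term to the imputation model for the CGI-C multiple-imputation sensitivity analysis, so that it still matches the analysis model.
- Use the existing screening fallback in SAP 5.1.3 for a missing baseline, and state how a patient with neither value is handled.
- Carry the term into the proportional-odds and logistic models, stating that the odds ratio is then conditional on baseline severity and so is a different quantity from the one now specified.
- Record the departure from Protocol 16.2.8 in SAP 5.10.

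No new data are needed. The costs are a short SAP edit, one degree of freedom if severity proves uninformative, and the rule for patients without any baseline value.

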5.3.3 Other Secondary Efficacy Variables

CGI-S (structured)

The analysis of the change from baseline to Visit 9 (“Month 6”) of CGI-S (structured) score will be performed similar to the analysis of the CGI-C score, modifying the approach using baseline as a covariate. The analysis for the extension treatment period will be performed in a similar way. For the extension treatment period, the change from baseline will be the change from the last assessment prior to first infusion in the study except for the placebo subjects who switch to EDS-EP at Visits 9 and 12 (“Month 6” and “Month 9”, respectively). For these subjects who are switched, the baseline will be the assessment just prior to the switch.

Ordinal logistic regression analyses will also be performed for CGI-S (structured) in a manner similar to CGI-C, with the exception that baseline CGI-S (structured) score will enter into the analysis.

The CGI-S score at baseline and all visits during the initial treatment period and extension treatment period (Visit 6, Visit 9, Visit 12, and Visit 15) will be summarized using summary statistics appropriate for continuous or categorical data by treatment group. The change from baseline to all visits will also be summarized and compared between treatment groups. Percent change from baseline will be summarized descriptively.

For the FAS only, the mean CGI-S score will be plotted over time during the initial treatment period with separate trend lines for each of the three treatment groups. This type of plot will be repeated for mean CGI-S score and mean change from baseline in CGI-S score over the entire study, with separate trend lines for the seven possible dosing schemes.

VABS

The analysis of the change from baseline (Day 0) to Visit 9 (“Month 6”) of VABS score will be performed using ANCOVA with LOCF score from baseline to Visit 9 (“Month 6”). Sensitivity analyses will be based on OC. The analysis for the extension treatment period will be performed in the same way. For the extension treatment period, the change from baseline will be the change from the last assessment prior to first infusion in the study except for the placebo subjects who switch to EDS-EP at Visits 9 and 12 (“Month 6” and “Month 9”, respectively). For these subjects who are switched, the baseline will be the assessment just prior to the switch.

The VABS score at baseline and all visits during the initial treatment period and extension treatment period (Visit 6, Visit 9, Visit 12, and Visit 15) will be summarized using summary statistics

appropriate for continuous data by treatment group. The change from baseline to all visits will also be summarized and compared between treatment groups.

For the FAS only, the mean VABS score will be plotted over time during the initial treatment period with separate trend lines for each of the three treatment groups. This type of plot will be repeated for mean VABS score and mean change from baseline in VABS score over the entire study, with separate trend lines for the seven possible dosing schemes.

5.3.4 Tertiary Efficacy Variables

The EQ-5D-5L scale will be used to assess QOL. The analysis of the change from baseline (Day 0) to Visit 9 (“Month 6”) of the EQ-5D-5L score will be performed in the same way as the analysis of change of VABS from baseline to Visit 9 (“Month 6”).

The EQ-5D-5L score at baseline and all visits during the initial treatment period and extension treatment period (Visit 6, Visit 9, Visit 12, and Visit 15) will be summarized using summary statistics appropriate for continuous data by treatment group. The change from baseline to all visits will also be summarized and compared between treatment groups. For the extension treatment period, the change from baseline will be the change from the last assessment prior to first infusion in the study except for the placebo subjects who switch to EDS-EP at Visits 9 and 12 (“Month 6” and “Month 9”, respectively). For these subjects who are switched, the baseline will be the assessment just prior to the switch.

For the FAS only, the mean EQ-5D-5L score will be plotted over time during the initial treatment period with separate trend lines for each of the three treatment groups. This type of plot will be repeated for mean EQ-5D-5L score and mean change from baseline in EQ-5D-5L score over the entire study, with separate trend lines for the seven possible dosing schemes.

